5.2. Treatment Assignment

Subjects will be assigned to study treatment in accordance with the randomization schedule generated prior to the start of the study by the study statistician, using the validated internal software RANDALL.

Each subject scheduled to receive study medication will receive a treatment allocation number when randomized. The randomization number will indicate which therapy the subject will receive, the treatment allocation ratio will be 2:1 (TQ/CQ: PQ/CQ). Once a randomization number has been allocated to a subject, it cannot be re-assigned to any other subject.

5.3. Blinding

This is a double-blind study and both subject and study staff will remain blinded to treatment.

The investigator or treating physician may unblind a subject's treatment assignment **only in the case of an emergency or in the event of a serious medical condition**, when knowledge of the study treatment is essential for the appropriate clinical management or welfare of the subject, as judged by the investigator. Investigators have direct access to the subject's individual study treatment. It is preferred (but not required) that the investigator first contacts the GSK Medical Monitor or appropriate GSK study personnel to discuss options **before** unblinding the subject's treatment assignment. If GSK study personnel are not contacted before the unblinding, the investigator must notify GSK as soon as possible, but without revealing the treatment assignment of the unblinded subject, unless that information is important for the safety of subjects currently in the study. The date and reason for the unblinding must be fully documented in the appropriate data collection tool.

GSK's Global Clinical Safety and Pharmacovigilance (GCSP) staff may unblind the treatment assignment for any subject with an SAE. If the SAE requires that an expedited regulatory report be sent to one or more regulatory agencies, a copy of the report,

identifying the subject's treatment assignment, may be sent to clinical investigators in accordance with local regulations and/or GSK policy.

5.4. Product Accountability

In accordance with local regulatory requirements, the investigator, designated site staff, or head of the medical institution (where applicable) must document the amount of investigational product dispensed and/or administered to study subjects, the amount returned by study subjects, and the amount received from and returned to GSK, when applicable. Product accountability records must be maintained throughout the course of the study.

5.5. Treatment Compliance

Compliance with study medication will be assessed in all subjects by directly observing the taking of medication for days 1-3 of the study. Compliance with respect to PQ medication/placebo in the subgroup of female subjects with moderate G6PD deficiency will be assessed for days 4-15 also by directly observing the taking of study medication. In all other subjects, outpatient compliance will be assessed by pill count and will be evaluated using details of dose administration recorded in the eCRF.

As part of the assessment of PQ compliance, levels of PQ and 7-carboxy PQ will be measured on Days 2, 3, 8 and 15 using TQ pharmacokinetic samples (see Section 6 and Section 6.6.1). Refer to the SPM for detailed methodology on measuring PQ and 7-carboxy PQ in these samples.

5.6. Concomitant Medications and Non-Drug Therapies

5.6.1. Permitted Medications and Non-Drug Therapies

5.6.1.1. Concomitant Medication

All subjects can be given paracetamol during the study but administration time must be recorded in the eCRF. Allowable antibiotics are penicillins, cephalosporins, carbapenems and aminoglycosides.

All concomitant medications (prescription and non-prescription) taken during the study should be recorded in the eCRF. The minimum requirement is drug name and date of administration.

5.6.1.2. Rescue Medication

Subjects requiring rescue medication will be given appropriate medication in accordance with site (local) or national treatment guidelines for *P. vivax* malaria or; e.g., *P. falciparum* malaria, whichever is applicable. Subjects offered rescue medication should be followed up for safety assessment until resolution of the malaria infection.

Details of rescue medication including reason for the rescue medication offered (e.g. withdrawal from study, treatment failure) should be recorded in the eCRF.

5.6.2. Prohibited Medications and Non-Drug Therapies

The following drugs are prohibited for use from 30 days prior to entry in the study through Day 180:

- Anti-malarials and other medicines with known anti-malarial activity.
- Drugs with hemolytic potential.
- Drugs known to prolong QTcF
- Drugs known to interact with primaquine or chloroquine.

Results from an *in vitro* renal transporters study showed that TQ inhibits the renal transporters MATE1, MATE2-K AND OCT2. Inhibition of these transporters may explain mild, transient, asymptomatic increases of creatinine observed in previous clinical studies and may lead to increased exposure to medications excreted via these transporters. The following drugs are prohibited for a period of 21 days immediately following the blinded dose of tafenoquine.

- The following anti-diabetic drugs of the biguanide class:
 - Phenformin
 - Buformin
- The following anti-arrhythmic drugs:
 - Dofetilide
 - Procainamide
 - Pilsicainide

Metformin, another biguanide anti-diabetic, may continue to be taken provided the subject has serum creatinine below the upper limit of normal and has no concomitant medical condition that increases the risk of lactic acidosis.

The use of herbal remedies during the course of the study is to be avoided. However, if taken this should be recorded in the eCRF under concomitant medication.

See [Appendix 5](#) in Section 11.5 for a non-exhaustive list of prohibited medicines for guidance.

5.7. Treatment after the End of the Study

There is no extension study planned and thus no post study treatment will be offered except for subjects diagnosed with malaria at the end of the study who will receive rescue medication outlined in Section [5.6.1.2](#)

The investigator is responsible for ensuring that consideration has been given to the post-study care of the patient's medical condition whether or not GSK is providing specific post study treatment.

5.8. Treatment of Study Treatment Overdose

An overdose for this study will be considered as any dose of study medication that is more than the planned dose on each dosing occasion.

Tafenoquine

No specific antidote for tafenoquine has been identified. In the event that overdose or toxicity occurs, individuals should be managed with appropriate supportive measures and clinical judgement. Immediate induction of emesis and/or gastric lavage is not recommended. Hemodialysis is unlikely to be clinically useful as tafenoquine is highly protein-bound.

Methemoglobinemia has been observed in clinical trials at therapeutic doses of tafenoquine; clinically significant levels could possibly be encountered in overdose.

Chloroquine

No specific antidote for chloroquine has been identified. In the event that overdose or toxicity occurs, individuals should be managed with appropriate supportive measures and clinical judgement. Immediate induction of emesis and/or gastric lavage is not recommended.

Drowsiness, blurred vision, diplopia, blindness, tinnitus, convulsions and coma can occur with overdose. Chloroquine is a known cardiovascular toxin thus cardiac monitoring and resuscitation facilities are essential. Thus in addition to dizziness, nausea, vomiting, diarrhea and headache hypotension, cardiogenic shock and cardiac arrest may occur. The 12 lead ECG may demonstrate decreased T waves, widening of the QRS complex, which may lead to ventricular tachycardia and/or fibrillation.

Primaquine

No specific antidote for primaquine has been identified. In the event that overdose or toxicity occurs, individuals should stop the medication and be managed with appropriate supportive measures and clinical judgement. Immediate induction of emesis and/or gastric lavage is not recommended.

Symptoms of primaquine overdose include abdominal cramps, vomiting, burning epigastric pain, central nervous system and cardiovascular disturbances, cyanosis, methemoglobinemia (see tafenoquine overdose guidelines), moderate leukocytosis or leukopenia and anemia.

6. STUDY ASSESSMENTS AND PROCEDURES

Table 2 Time and Events

Protocol Activity	Visit Day															
	Screening/Treatment Period ^a							Follow-Up Period							Relapse Visit ^b	Withdrawal Visit ^c
	Day 1 ^d	Day 2	Day 3	Day 5 +1d	Day 8 -/+1d	Day 11 -/+1d	Day 15 -/+2d	Day 22 -/+3d	Day 29 -/+3d	Day 60 -/+7d	Day 90 -/+7d	Day 120 -/+10d	Day 150 -/+10d	Day 180 -14/+21d	Relapse	Withdrawal
Window																
Informed Consent Process	X															
Demographic Information	X															
Initial History Only ^e	X															
Physician Assess. Malaria Signs & Symptoms	X															
Inclusion/Exclusion Criteria	X															
Efficacy Assessments																
Parasitological Assessment (blood smear)	X ^f	X ^f	X ^f		X		X	X	X	X	X	X	X	X	X	X
Plasmodium PCR Genotyping	X														X	
Plasmodium whole genome sequencing	X														X	
Safety Assessments																
Review Concomitant Medications	X	X	X	X	X	X	X	X	X	X	X	X	X	X	X	X
Vital Signs ^g	X	X	X		X	X	X	X	X	X	X	X	X	X	X	X

Protocol Activity	Visit Day															
	Screening/Treatment Period ^a							Follow-Up Period							Relapse Visit ^b	Withdrawal Visit ^c
	Day 1 ^d	Day 2	Day 3	Day 5	Day 8	Day 11	Day 15	Day 22	Day 29	Day 60	Day 90	Day 120	Day 150	Day 180	Relapse	Withdrawal
Window				+1d	-/+1d	-/+1d	-/+2d	-/+3d	-/+3d	-/+7d	-/+7d	-/+10d	-/+10d	-14/+21d		
Physical Examination	X	X	X		X		X	X	X	X	X	X	X	X	X	X
ECG w/ Interpret. & Report ^h	X	X							X						X	X
Adverse Events Assessment ⁱ	X	X	X	X	X	X	X	X	X	X	X	X	X	X	X	X
Serious Adverse Events ^j	X	X	X	X	X	X	X	X	X	X	X	X	X	X	X	X
G6PD (phenotyping) ^k	X									X		X				
G6PD and CYP2D6 (genotyping)		X														
Ophthalmological Exam (qualified sites only)	X								X		X			X ^l		X
Laboratory Assessments																
Hematology ^m	X		X ⁿ	X	X	X	X	X	X	X	X	X	X		X	X
Clinical Chemistry ^o	X		X ⁿ	X	X	X	X	X	X	X	X	X			X	X
Methemoglobin	X	X	X	X	X	X	X	X	X	X		X		X	X	
Urinalysis ^p	X		X	X	X	X	X	X	X	X	X	X		X	X	
Blood Draw for PGx		X ^q														
Pregnancy Test ^r	X						X		X	X				X	X	X
Health Outcomes																
Health Outcomes Assessments ^s	X						X	X ^t	X ^t	X ^t	X ^t	X ^t	X ^t	X ^t	X ^t	X ^t

Protocol Activity	Visit Day															
	Screening/Treatment Period ^a							Follow-Up Period							Relapse Visit ^b	Withdrawal Visit ^c
	Day 1 ^d	Day 2	Day 3	Day 5	Day 8	Day 11	Day 15	Day 22	Day 29	Day 60	Day 90	Day 120	Day 150	Day 180	Relapse	Withdrawal
Window				+1d	-/+1d	-/+1d	-/+2d	-/+3d	-/+3d	-/+7d	-/+7d	-/+10d	-/+10d	-14/+21d		
Pharmacokinetic Assessments																
PK/PD Sampling ^u		X	X		X		X		X	X					X	
Investigational Product																
Dispense Open Label Chloroquine	X	X	X													
Dispense Blinded Study Medication	X ^v	X ^v														
Treatment Compliance Int. - Invest.	X	X	X	X	X	X	X									
IVRS Registration	X															

- a All subjects must remain hospitalized for Days 1 through 3.
- b Subjects who relapse will continue to be monitored for safety and efficacy at all scheduled visits through day 180. Relapse is defined by a positive blood smear with or without vivax symptoms.
- c If subjects withdraw from blinded study medication, all scheduled follow-up visits should be performed to conduct safety assessments up to and including Day 180.
- d Visit Day 1 includes all screening procedures and the first day of treatment with study medication.
- e Includes medical, disease and therapy histories.
- f Blood smears are to be taken twice a day, 6-12 hours apart for the first 3 days, or until 2 consecutive negative thick blood smears are obtained.
- g Vital signs include height and weight (screening only), blood pressure, temperature, heart rate and respiratory rate. Vital signs are to be performed twice a day on Days 1 through 3, at least 4 hours apart, and immediately prior to PK measurements.
- h ECGs are to be performed at screening (in triplicate), 12 hours after the first dose of blinded study medication, and on Day 29.
- i Adverse events are recorded from the time of the first dose of study medication.
- j Serious adverse events are recorded from the time of consent in order to fulfil international regulatory requirements.
- k G6PD phenotyping to be performed by quantitative spectrophotometric analysis. One or more G6PD rapid point of care tests may be performed at baseline (Day 1) only.
- l Only if Day 90 ophthalmological exam shows abnormalities.
- m Hematology includes hemoglobin, hematocrit, red blood cell/white blood cell/platelet counts, mean cell volume, white blood cell differential and reticulocyte count.

- n Hematology and clinical chemistry on Day 3 must be reviewed prior to discharge from the hospital.
- o Clinical Chemistry includes CPK, BUN, serum creatinine, total and indirect bilirubin and liver clinical chemistry.
- p Mid-stream urine will be analyzed for protein, glucose, ketones, bilirubin, blood, nitrites, urobilinogen and leukocyte esterase by dipstick method.
- q The pharmacogenetics sample must be collected at the earliest opportunity after randomization and during the in-clinic treatment visit (Days 1-3).
- r Serum or urine pregnancy test that is routinely used at site with a test sensitivity for hCG level ≤ 25 mIU/mL. FSH serum test only for post-menopausal females with less than 6 months spontaneous amenorrhea.
- s Refer to Section 6.5 of the protocol for details on health outcome data collection.
- t Health outcomes assessments will only be collected at these visits from subjects with confirmed parasitemia or from subjects with clinically relevant hemolysis.
- u Day 2 and Day 3 PK samples must be taken 6-12 hours and 24-48 hours post TQ dose.
- v Treatment with blinded study medication will begin on either Day 1 or Day 2.

6.1. Critical Baseline Assessments

Written, dated informed consent must be obtained from each potentially eligible subject (or his/her legal representative) by study site personnel **prior** to the initiation of any screening procedures.

Clinical and laboratory assessments will be conducted at screening (**prior to first dose of the study medication**) as detailed in the Time and Events ([Table 2](#)).

- Demographic data will be collected to include details of date of birth, gender, race and ethnicity
- Medical history will be collected

- A physical examination will be conducted including:
 - Cardiovascular examination
 - Abdominal examination including assessment of splenomegaly
 - Respiratory examination

- Vital signs will be assessed. These include height, weight, temperature (oral, axillary or tympanic), heart rate, respiratory rate, systolic and diastolic blood pressure

- Investigators will assess *P. vivax* malaria symptoms at baseline. The incidence and severity (defined as absent, mild, moderate, severe, or unknown) of the following symptoms will be recorded: chills and rigours, headache, dizziness, abdominal pain, anorexia, nausea, vomiting, diarrhea, pruritis or itching, and coughing. The date of onset of symptoms will also be recorded. The investigator or designee can also assess and record any other *P. vivax* malaria symptoms.

- Blood smears for parasitological assessment will be collected and examined for asexual parasite count and gametocyte blood count (see Section [6.3](#) and the SPM for further details).

- A blood sample will be collected on a filter paper and stored for future plasmodium genotyping analysis. An additional blood sample will be collected to conduct exploratory plasmodium whole genome sequencing.

- Current and prior medications will be reviewed including any anti-malarial medication that has been used.

- G6PD status will be assessed using quantitative spectrophotometric analysis (further instructions can be found in the SPM). The quantitative analysis will

be used to determine the subject's eligibility for the study. One or more G6PD rapid point of care tests may also be performed at baseline.

- Periodic external quality assurance testing will be performed to ensure high quality G6PD assay data. Procedures for quality assurance will be described in detail in the SPM.
- A blood sample will be collected on Day 2 for G6PD and CYP2D6 genotyping.
- Laboratory Assessments:
 - Hematology analysis will include: Hb, hematocrit (Hct), red blood cells (RBC), mean cell volume (MCV), differentiated white blood cells (WBC), platelets and reticulocytes (for conversion to absolute).
 - Clinical chemistry evaluations will include: blood urea nitrogen (BUN), serum creatinine, total and indirect bilirubin and liver chemistries (alanine aminotransferase (ALT), aspartate aminotransferase (AST), alkaline phosphatase (ALP) and creatine phosphokinase (CPK))
- A serum or urine pregnancy test will be performed that is routinely used at the site, provided the test has a sensitivity for hCG of ≤ 25 mIU/mL. A FSH serum test will be performed only for post-menopausal females with less than 6 months spontaneous amenorrhea.
- Methemoglobin levels will be assessed using a non-invasive signal extraction CO-Oximeter handheld machine.
- 12 lead ECG will be performed with the subject in a semi-supine position having rested in this position for at least 10 minutes beforehand. Measurements that deviate substantially from previous readings will be repeated immediately. Three (3) measurements will be taken at screening, five minutes apart.
 - The mean hear rate, RR interval, QRS duration, QT interval and QTcF (QT corrected by Friderica's formula) will be calculated from automated ECG readings and abnormal findings will be recorded. The mean value recorded pre-dose will be classified as baseline.
- A subset of qualified sites will perform the following ophthalmic assessments during in-patient stay and prior to randomization:
 - Visual acuity and color vision will be assessed by standard methods

- Humphrey 10-2 visual field in order to determine the threshold sensitivity of specific loci in the central retina, detection and definition of relative or absolute scotomas.
- Slit lamp examination of the cornea (to document and grade any corneal deposits), lens and retina.
- Retinal digital photography for the documentation of changes in the retinal morphology.

6.2. **Unscheduled Visits**

Subjects who have one or more visits outside the allowable time window defined for each scheduled visit (see [Table 2](#)) will undergo all the procedures and assessments described in [Table 2](#) with the exception of assessments performed only at screening and the PK assessments. Subjects should be able and/or encouraged to return to the clinic for unscheduled visits at anytime during the 180-day study period. **In addition, subjects must return to the clinic anytime they are experiencing a recurrence of malaria symptoms.**

6.3. **Efficacy**

Parasitology

Asexual parasite counts:

Microscope blood slides will be prepared pre-dose at screening on Day 1, post-dose on Day 1, then twice a day, 6-12 hours apart for the first 3 days, or until 2 consecutive negative thick blood smears are obtained. Where the subject receives CQ <6 hours from midnight on day 1, a post dose slide can be taken early on day 2. Microscope blood slides will be prepared at subsequent visits on Days 8, 15, 22, 29, 60, 90, 120, 150 and 180. In addition, blood films should be obtained whenever parasitological re-assessment is required and at the relapse visit or withdrawal visit as applicable. At each time point two thick and one thin film slide should be prepared on separate slides and one additional unstained slide with both thick and thin films retained for quality control. For detailed instructions on the methodology for staining and counting please refer to the SPM.

In summary:

Thick film parasitemia (malaria parasite density) should be calculated first, using the subjects' actual white blood cell count (WBC). Aim to count the number of parasites per 200-250 WBCs:

$$\text{i.e., D1 parasitemia}/\mu\text{L} = (\text{number of D1 parasites}/\text{D1 WBC counted}) \times \text{D1 WBC count}$$

If after 200 WBCs have been counted, 9 or fewer parasites have been identified, continue counting until reaching 500 WBCs.

If the thick film contains > 250 asexual parasites per 50 WBC (i.e. 5 parasites per WBC, equivalent to 40,000 asexual parasites/ μL), 8 high power fields on the thin film should be

read and parasites counted against (assuming 250 RBC per high powered field = 2000) red blood cells counted (RBCs).

Parasitemia from thin films is then calculated as:

$$\text{Parasitemia}/\mu\text{L} = (\text{number of parasites in 8 high powered fields} / \text{RBC counted} = 2000) \times 4,000,000 [\text{assumed RBC}]$$

The calculated parasitemia/ μL will be recorded into the eCRF for each time point. See SPM for quality control procedures.

Local quality control of slides is performed by reading of the slide by 2 different qualified microscopists. If the results from the two readings are within 20% of each other for the parasite count and the two readers agree on the species identification then the average result from the two microscopists is computed and recorded in the eCRF.

If the results from the two microscopists are different by more than 20 % or they disagree on the species identification then a third independent reader is required who will read both slides. The average count from the third independent reader is compared with results from the first two readers. The count of the first two readers closest to the average count of the third independent reader is regarded as final and should be recorded in the eCRF. The third reader should therefore be a highly experienced malaria microscopist.

Slides are considered negative after review of 100 high-power fields.

Gametocyte counts

In the same way, thick film slides will be read for gametocytes on Day 1 (pre-dose and post-dose) and then twice daily for the remainder of the in-patient stay. Slides will be prepared at subsequent visits on Days 8, 15, 22, 29, 60, 90, 120, 150 and 180 (and relapse and withdrawal visits if applicable). If gametocytes are present they will be counted against a 200-250 WBCs and their density calculated as follows:

$$\text{Gametocytes}/\mu\text{L} = (\text{number of gametocytes}/\text{WBC counted}) \times \text{WBC count}$$

Parasite Genotyping

Two drops of peripheral blood will be collected onto pre-printed filter paper for subsequent DNA extraction and PCR analysis of *Plasmodium* species on all subjects at screening (Day 1; pre-dose) and; if necessary, at the time of the first recrudescence/relapse or re-infection.

PCR of the *P. vivax* genes, such as *PvMSP-1*, *PvCSP* and *PvAMA-1*, as well as any other markers deemed appropriate, will be used to distinguish between genetically homologous and genetically heterologous infection.

Parasite whole genome sequencing

Four milliliters of blood will be taken for subsequent parasite exploratory whole genome sequencing at baseline and at the relapse visit. If the time taken to transport samples to

the central laboratory leads to poor yields of high quality sequencing data (judged after n=50 samples have been analyzed) then this exploratory sample will no longer be taken.

External quality control

External quality control of slide readings will be conducted by an independent laboratory. The external quality control will be blinded to the treatment assignment. They will examine a proportion of slides from each study site. The procedure for quality control will be described in the SPM.

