13.6.4. Efficacy**Relapse free efficacy and Time to Relapse****Six months**

- A subject will be considered to have demonstrated relapse-free efficacy at 6 months for the purposes of the analysis if **all** of the following are true (also described in the flowchart below):
 - Subject had a non-zero *P. vivax* asexual parasite count at baseline. Subjects with no asexual *P. vivax* parasites at this time point will be censored with time to relapse = 0 days.
 - Subject demonstrated initial clearance of *P. vivax* parasitaemia. This is defined as two negative asexual *P. vivax* parasite counts, with at least 6 hours between the counts, and no positive counts in the interval. Subjects who do not meet this criteria will be classified as relapses, with time to relapse = 0 days.
 - Subject has no positive asexual *P. vivax* parasite count at any assessment prior to or on Study Day 201 following initial parasite clearance. Subjects who do have a positive count will be classified as relapses, with time to relapse = (date of first positive count) – (date of Study Day 1) days.
 - Subject did not take a concomitant medication with anti-malarial activity at any point between Study Day 1 and their last parasite assessment. A list of all concomitant medications will be reviewed by a GSK clinician prior to unblinding the study, and classified accordingly. Subjects who did take a drug with anti-malarial activity but never had a positive asexual *P. vivax* parasite count after initial clearance will be censored, with time to relapse censored at (date of last negative parasite assessment prior to concomitant medication start) – (date of Study Day 1). If a subject has not had a negative assessment prior to the concomitant medication start date, they will be censored at 0.
 - Subject is parasite-free at 6 months. This is defined as a negative asexual *P. vivax* parasite count at the first parasite assessment performed on or after Study Day 166.
- Subjects who do not have a positive asexual *P. vivax* parasite count following initial clearance but where the final parasite count occurred before Study Day 166 will not have been classified by the preceding rules. These subjects will be considered to be censored, with time to relapse censored at (Date of final parasite assessment) – (date of Study Day 1).

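### The third-reader rule can record a slide as negative when two of three readers saw parasites, and it does not say whose species call stands

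*Supplement*

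**What the plan says.** Protocol Amendment 5, Section 6.3 (Asexual parasite counts), has each slide read by two microscopists. If their counts lie within 20% of each other and they agree on species, the average goes into the eCRF. A third reader is called in as follows: "If the results from the two microscopists are different by more than 20" per cent, "or they disagree on the species identification then a third independent reader is required who will read both slides". The resolution is then: "The count of the first two readers closest to the average count of the third independent reader is regarded as final".

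Two related provisions stand nearby. A negative slide is defined by "Slides are considered negative after review of 100 high-power fields", and for low counts the instruction is "If after 200 WBCs have been counted, 9 or fewer parasites have been identified, continue counting until reaching 500 WBCs". The section refers to the Study Procedures Manual (SPM) for quality-control procedures and provides for external checking of a proportion of slides.

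The counts then go straight into the endpoints. In the Reporting and Analysis Plan (RAP, Amendment 1), Section 13.6.4, a subject is relapse-free at six months only with no positive asexual *P. vivax* "parasite count at any assessment prior to or on Study Day 201 following initial parasite clearance". Initial clearance is two negative counts at least 6 hours apart with no positive between them. Neither definition has a confirmation or adjudication step. Section 8.2 of the meta-analysis plan uses the same definitions.

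**The concern.** Relapse and clearance turn on whether *P. vivax* asexual parasites are present. The disagreement rule is written for how many there are. A reader who sees none and a reader who sees a few always differ by more than 20%, so every positive/negative split goes through a rule that measures numerical distance and ignores how many readers saw parasites.

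A low-density recurrence recorded as 0 is missed at that visit. From Day 60 the scheduled visits are 30 days apart, so detection may slip by about that long. A false 0 during the first days can also provide one of the two negatives that define clearance.

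On species, the rule names a disagreement as a reason for a third read and then gives no way to settle it.

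**Working it through.** The plan states no error rate for this rule, so there is no figure to reproduce. I applied the rule as written and then gauged its size under a stated assumption.

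**Step 1: the rule.** Call the first two reads A and B and the third reader's average C. The rule records A if |A − C| < |B − C|, and B if the inequality is reversed. Put A = 0 and B = b > 0:

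- 0 is recorded when C < b − C, that is, when C < b/2;
- b is recorded when C > b/2;
- C = b/2 is a tie with no stated outcome.

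So for every 0 < C < b/2, two of three readers are positive and the record is negative. If C = 0, the record is 0, which agrees with the two-of-three majority. The rule therefore overrides the majority only towards negative.

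**Step 2: worked cases** (parasites/µL). The protocol's own equivalence, "i.e. 5 parasites per WBC, equivalent to 40,000 asexual parasites" per µL, implies 40,000 / 5 = 8,000 white cells/µL, so 1 parasite per 500 white cells is 8,000 / 500 = 16/µL.

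| Reader 1 | Reader 2 | Third | Recorded |
|---|---|---|---|
| 0 | 48 | 16 | 0 |
| 0 | 96 | 32 | 0 |
| 0 | 160 | 48 | 0 |
| 0 | 32 | 16 | tie, no rule |
| 0 | 160 | 96 | 160 |

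**Step 3: size, under an assumption.** Suppose all reads are independent Poisson counts per 500 white cells with a common mean λ, and a zero count is a negative read. The first two readers then split positive/negative with probability 2e^(−λ)(1 − e^(−λ)); at λ = 1 this is 2 × 0.3679 × 0.6321 = 0.465. The text can mean that C is one count or the mean of two slides, so both are shown. For one count, the chance of a recorded negative against a positive majority is 2e^(−λ) Σ p(b) Σ p(c) over 0 < c < b/2; at λ = 1 this is 2 × 0.3679 × 0.0302 = 0.022.

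| λ (density/µL) | Split | Majority positive but recorded negative, % of all slides (one count / mean of two) | Same, % of split slides where the third reader is positive | Ties, % of all slides |
|---|---|---|---|---|
| 1 (16) | 46.5% | 2.2 / 7.1 | 7.6 / 17.8 | 5.2 / 11.9 |
| 1.5 (24) | 34.7% | 3.1 / 5.7 | 11.4 / 17.2 | 4.3 / 6.4 |
| 2 (32) | 23.4% | 2.8 / 3.6 | 13.7 / 15.6 | 2.7 / 3.2 |
| 3 (48) | 9.5% | 1.4 / 1.1 | 15.0 / 12.1 | 0.8 / 0.8 |
| 6 (96) | 0.5% | 0.05 / 0.03 | 11.0 / 6.0 | 0.02 / 0.02 |

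**Step 4: higher densities.** There the rule bites only if a reader misses the slide altogether. Given such a miss, the chance that C < b/2 is about 2–5% if the between-read coefficient of variation is 30%, 10–15% at 50%, and 21–28% at 100% (assumed values).

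**Step 5: species.** Take vivax 500, falciparum 300, and a third read of vivax 350. The nearest count is 300, from the reader outvoted on species. The protocol makes the 300 final and does not say which species is recorded with it.

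**The case against.** Several objections limit the point.

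- **Species.** A reader might infer that the rule settles species by density, so that the outvoted reader's species wins. The documents do not support that. They fix only the count and are silent on the species call. Species PCR is also sampled at the first recurrence, which gives a second source for a positive slide of disputed species, though nothing says PCR overrides microscopy.
- **Size.** A reader might take the 12–18% figures at means of 1–3 (mean of two slides) as the share of slides misread. They apply only to split slides where the third reader is also positive. Over all slides they become about 7%, 4% and 1%. The model also equates zero per 500 white cells with a negative read, whereas the protocol's criterion is 100 high-power fields and the two are not linked. No document gives a discordance rate or says how many recurrences present at such densities.
- **Bias between arms.** A reader might infer that one arm is favoured. Treatment is double-blind, so errors should fall alike on both arms, and non-differential missed events leave a ratio roughly unbiased.
- **Consequences.** A missed slide is often only a delay. Subjects must return if symptoms recur, and any later positive through Study Day 201 still counts. One false zero does not establish clearance.
- **The SPM.** It is not shown and may hold more detail.

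These points narrow the reach but leave the core standing. The protocol itself says which value is final, so an unseen SPM cannot be assumed to override it. External quality control covers only a proportion of slides, with nothing saying that its reading replaces the eCRF value. PCR at a recognised recurrence cannot correct a slide recorded as negative.

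**Conclusion.** The point holds in limited form. That the rule can record a negative against a two-of-three positive majority, and leaves ties open, follows from its wording and needs no model. The missing species rule is a gap in the text, not a wrong rule.

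How often this happens rests on assumed Poisson reads with a shared density: a peak of about 3% (single third count) to 7% (mean of two slides), falling to 0.05% or less at 96/µL. The number of affected subjects cannot be estimated from the documents. The effect is to miss or delay relapse and possibly make clearance look earlier, in the secondary efficacy endpoints and the time-to-relapse meta-analysis. No distortion of the treatment comparison has been shown.

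**What to change.** Split the rule in Section 6.3 and in the SPM:

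1. **Presence or absence, and species:** the final result is the majority of the three reads.
2. **Density:** apply the nearest-count rule only between reads that agree on positivity and species. If the third reader sides with the positive reader, record that reader's count.

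This brings recorded negatives against a positive majority to zero by construction and disposes of the b/2 tie. The text should also say what counts as a positive third read when two slides are read, and name a fallback if all three readers differ on species.

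The cost is a sentence or two and retraining of slide readers, with no extra reads. The downside is real but small. One positive makes a relapse without confirmation, so a few more isolated low-density positives would count. If some are false and non-differential, they pull a hazard ratio towards 1, which is the favourable direction for the non-inferiority comparison, so the number of relapses resting on a split read should be reported.
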